12. DATA AND SPECIMEN BANKING*

A limited data set will be securely stored for potential future use by the Principal Investigator. A limited dataset may be shared with study collaborators (with an executed Data Use Agreement) or with study funder/sponsors. A de-identified (by HIPAA standards) dataset may be made available to the public with PI approval; a data dictionary will be submitted to the IRB for review/approval prior to sharing the de-identified dataset.

13. Data Analysis and Management*

All patient-facing data collection materials will be submitted to the IRB for review and approval prior to use in the study. EHR and MyChart audit log data will be collected as described in the ISP, consent/fact sheet, HIPAA authorization/waiver materials reviewed and approved by the IRB.

Power analysis: The goal of this feasibility pilot is to determine the acceptability of the intervention and to estimate important process parameters (i.e. recruitment rates, completion rates of components) to inform a future study, including designing or refining outcome measures. As such, we have not conducted a sample size calculation.

Data analysis plan: To evaluate feasibility of Tele-Navi LCS, we will study process measures and effectiveness. Data sources include field notes, patient surveys, patient and provider interviews, Electronic Health Record (EHR) chart review, EHR administrative data and recording of telehealth coaching and a video-call. We will employ a mixed-methods process-outcomes pathway analysis.

Quantitative analysis: For measures of outcomes and intervention fidelity, we will present summary statistics with means and standard deviations of study variables. Further, we will create useful visualizations, including treatment cascades – a common graph used in quality improvement to identify gaps in the flow of patients to treatment (or follow-up screening and post-LDCT patient-provider communication in this case).

Qualitative analysis: We will analyze patient and provider interview transcripts to evaluate the acceptability of Tele-Navi LCS, understand their experiences, and elicit suggestions for improvement. Our analysis will be informed by constructs from the SCT, PRISM, and STM.

INVESTIGATOR STUDY PLAN - REQUIRED

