4. OBJECTIVES*

The main purpose of our study is to develop Tele-Navigation of Lung Cancer Screening (Tele-Navi LCS) – an intervention that is designed to improve patient awareness about the importance of LCS follow-up and to promote patient-provider communication about low-dose CT (LDCT) results, with the ultimate goal of increasing adherence to LCS. Our study has two specific aims:

Aim 1: Develop Tele-Navi LCS, using a co-production approach with patients at UMMH, and refine Tele-Navi LCS based on feedback from LCS stakeholders at UMMH, Wake Forest, UCHealth, and UPenn.

Aim 2: Pilot test Tele-Navi LCS and evaluate its feasibility, acceptability, and associated costs by implementing it in the clinical LCS workflow in primary care clinics at UMMH.

Because the data collected in Aim 1 may influence the activities of Aim 2, we will develop the majority of Aim 2 study materials at a later time. Aim 2 recruitment activities will not commence until these materials have been submitted to the IRB for review and approval.

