10. STUDY ENDPOINTS*

Primary outcomes are adherence to follow up LDCT and feasibility of Tele-Navi LCS. Adherence is defined as LDCT completion at 3, 6 and 12 months from the due date (as in previous studies; this definition may change depending on the status of COVID pandemic) and will be measured by EHR data.^{7,8,10-12} For feasibility, we will assess how engaged patients are during telehealth coaching, video-calls by tele-navigator, telehealth visit and patient portal use. We will assess intervention fidelity by recording and comparing all telehealth coaching and video-calls by a tele-navigator against a pre-defined checklist of key elements.

Secondary outcomes are occurrence of patient-provider communication after LDCT; communication modality used; contents of the communication assessed by EHR review and a patient survey; patient understanding of the result of LDCT and follow-up plan assessed by patient surveys; and perception and acceptability of the intervention from patient surveys and

INVESTIGATOR STUDY PLAN - REQUIRED

interviews and provider interviews. We will also measure cost by tracking time required for training for a Tele-Navigator, all the intervention components provided by the Tele-Navigator, and time and any other resources required to implement Tele-Navi LCS into clinical workflow.

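### Adherence is timed from the due date but Aim 2 enrols only patients already overdue, so some windows may close before the intervention starts; the planned means and SDs show neither this nor the precision.

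*Combined protocol and SAP*

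**What the plan says.** **Outcome.** Section 10: "Primary outcomes are adherence to follow up LDCT and feasibility of Tele-Navi LCS". It continues: "Adherence is defined as LDCT completion at 3, 6 and 12 months from the due date". The data come from the EHR, and a parenthesis allows the definition to change with the state of the pandemic. Section 10 does not say which due date is meant.

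**Who enters.** Section 6 requires Aim 2 patients to be overdue for their follow-up scan and sets no upper limit on the time past due. Section 11 adds purposeful sampling. Section 25 plans about 20 intervention patients and about 5 interviewed providers, roughly 25 people in all.

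**Analysis.** The data analysis plan in Section 13 begins: "To evaluate feasibility of Tele-Navi LCS, we will study process measures and effectiveness". Outcome and fidelity measures are to be summarised by means and SDs, supplemented by treatment cascades and a mixed-methods pathway analysis. No confidence interval is planned, no comparator is described, and nothing records how many patients still had a given window open when they enrolled.

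**Stated purpose.** Section 4 sets Aim 2 to "evaluate its feasibility, acceptability, and associated costs", within a project "with the ultimate goal of increasing adherence to LCS". The power paragraph in Section 13 says "The goal of this feasibility pilot is to determine the acceptability of the intervention", together with estimating process parameters for a later study, and concludes: "As such, we have not conducted a sample size calculation".

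**The concern.** The clock for adherence starts at the due date, and every Aim 2 patient enters after it. Suppose the due date is that of the missed scan. A patient who enrols four months late has then already failed the 3-month criterion, and one who enrols more than a year late has failed all three. These results are settled before the tele-navigator calls, so they say nothing about the intervention, yet they stay in the denominator and pull the all-enrolled rate down.

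Recruitment itself uses up window time. Section 24 has an invitation, about a week's wait, then calls over two to three weeks, which is up to about 3 to 4 weeks before consent for patients who do not respond at once.

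At stake is the adherence figure handed to the next study. Without the number at risk, a low rate could reflect late enrolment or a weak intervention, and a reader could not tell which. Without an interval, a rate from about 20 people can look more exact than it is. And if it is reported as a finding about effectiveness, it will be asked to bear a meaning that one small volunteer group cannot support.

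**Working it through.** The plan gives no power, effect size or derived sample size, so there is no stated figure to reproduce. The checks below use n = 20 from Section 25.

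**1. Ceiling on 3-month adherence.** Let c be the number of patients already more than 3 months past due at enrolment. The highest possible all-enrolled rate is (20 − c)/20. The documents give no value for c; the values here are assumptions.

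| c (assumed) | Ceiling |
|---|---|
| 0 | 20/20 = 100% |
| 5 | 15/20 = 75% |
| 10 | 10/20 = 50% |
| 15 | 5/20 = 25% |

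The same formula applies at 6 and 12 months with the matching c, which can only be equal or smaller.

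**2. Effect of the denominator.** All-enrolled rate = (share with window open) × (rate among those open). With c = 10 and 5 of the 10 open windows met (both assumed), this is 10/20 × 5/10 = 5/20 = 25%. Over patients with the window open it is 5/10 = 50%. The same patients give either figure.

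**3. Precision.** Exact (Clopper–Pearson) 95% limits for x of n are the 0.025 quantile of Beta(x, n − x + 1) and the 0.975 quantile of Beta(x + 1, n − x). The SD of a 0/1 variable is √[n/(n − 1) × p(1 − p)].

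| x/n | Mean (SD), as planned | Exact 95% CI | Width, points |
|---|---|---|---|
| 5/20 | 0.25 (0.44) | 8.7–49.1% | 40.4 |
| 10/20 | 0.50 (0.51) | 27.2–72.8% | 45.6 |
| 15/20 | 0.75 (0.44) | 50.9–91.3% | 40.4 |
| 5/10 | – | 18.7–81.3% | 62.6 |

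For 10/20 the SD is √(20/19 × 0.25) = 0.513. Given n, the SD is fixed by the proportion, so it adds nothing to it; 5/20 and 15/20 even share the same SD.

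**4. Whether the rate can speak to effectiveness.** Section 5 cites adherence of 16–59% in community programs and above 80% in comprehensive ones, but the plan names neither as a benchmark. An observed 12/20 = 60% has an exact 95% CI of 36.1–80.9%, which takes in the upper part of the first range and just reaches beyond 80%. More basically, with no comparator, unassisted return and volunteer selection cannot be separated from an intervention effect at any sample size.

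**5. Single group.** Section 25's counts (20 patients + 5 providers = 25) leave no room for enrolled controls, and the text describes no randomisation or historical comparison. Section 24 refers once to an intervention group, and the Aim 2 figure is not available here. Single-group status is therefore an inference. The counts could not reveal an unenrolled records comparison, but none is described.

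**The case against.** **The due date may not be the missed one.** Section 10 does not specify it, and Sections 9 and 11 plan record review of annual follow-up for up to 4 years. Later due dates would have windows that were open at entry. This stands as a qualification, and it is why the first step is to name the due date. It does not remove the problem under the natural reading, and capturing late scans does not settle who was at risk for a given window.

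**The size rests on assumed counts.** This stands in full. If most patients are only slightly overdue, the effect is small.

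**The plan already has suitable summaries.** The mean of a yes/no variable is its proportion, cascades normally show counts by step, and a reader given n/N can compute an interval. That is fair, and makes the missing interval a modest point by itself. A cascade still does not show how many windows were open at enrolment, and a reader cannot recover that number.

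**Stronger readings.** A reader might infer that Sections 4, 10 and 13 contradict each other on the purpose of Aim 2, since Section 10 makes adherence primary and lists "perception and acceptability of the intervention from patient surveys" as secondary. The documents do not support that much. Section 4 and the power paragraph are compatible, feasibility is itself a primary outcome, and in a plan with no test or success rule the ranking changes no analysis. A reader might also infer that the study claims to demonstrate effectiveness. The word appears once here, inside a sentence about feasibility; it is not equated with adherence, and no conclusion about effect is promised. Nor is the absence of a sample size calculation an error in a feasibility pilot.

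**Conclusion.** The concern holds as a matter of definition and reporting. Measuring adherence in this pilot is reasonable. But, if the due date is that of the missed scan, the plan as written can count patients as non-adherent on windows that closed before the intervention began, and its planned summaries would not reveal it.

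The direction is known: closed windows lower the all-enrolled rate. The amount is not. The 75%, 50% and 25% ceilings and the 25% versus 50% contrast are illustrations on assumed counts, so it would go too far to say that the adherence result will be badly distorted. The precision figures depend only on n of about 20: for 5, 10 or 15 adherent patients the exact 95% interval is 40 to 46 points wide.

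That the rate cannot show effectiveness rests on the inference that there is one group with no comparator.

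**What to change.** **Section 10.** State which due date applies to a patient who is already overdue at entry.

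**Section 13.**
- Report adherence at each time point as n/N of all enrolled patients with an exact 95% CI, in place of a mean and SD.
- For each of the three windows, also report how many patients had it open at enrolment and how many of those completed LDCT, with an exact 95% CI.
- In the opening sentence of the data analysis plan, change the object of study to *process measures and descriptive clinical outcomes*, and add: *No conclusion about effectiveness will be drawn from the single-group adherence rate.*

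Re-ranking adherence and acceptability in Section 10 is optional.

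**Cost.** Wording only, with no new data collection: the due date is needed to define adherence, the consent date is documented (Section 30), and scan completion already comes from the EHR. The drawbacks are small denominators for windows that few patients have open and a less prominent headline for adherence. The all-enrolled denominator is kept, so no patient is dropped.

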6. INCLUSION AND EXCLUSION CRITERIA*

Patient Participants

Inclusion Criteria:

- Is eligible for LDCT for LCS follow-up
- Has technology to complete study activities (e.g., video call visit)
- English speaker

Aim 1 Additional Inclusion Criteria:

- Has UMMH PCP
- Has undergone LCS at UMMH in the past three years

Aim 2 Additional Inclusion Criteria:

- Has undergone LCS at UMMH
- Is overdue for LDCT follow-up

INVESTIGATOR STUDY PLAN - REQUIRED

Exclusion Criteria:

- Has previous diagnosis of lung cancer
- Has active cancer diagnosis
- Is a nursing home or group care resident
- Is pregnant

Stakeholder/Provider Participants

Inclusion Criteria Aim 1:

- Age ≥ 18
- Primary care provider/IT leader/lung cancer screening program leader/lung cancer screening navigator
- Works at UMass Memorial Health, Wake Forest Baptist Health, UCHealth, or UPenn

Inclusion Criteria Aim 2:

- Age ≥ 18
- Primary care provider
- Works at UMass Memorial Health

Vulnerable Populations

The following populations **will not be included** in this study:

- Individuals who are not yet adults (infants, children, teenagers)
- Pregnant women
- Adults unable to consent
- Prisoners

Since this is a small-scale study (~65 total subjects in 4 groups, with 3 different interviews and one intervention) it is not possible to have the study materials translated into other languages. If this pilot study shows promise, larger follow-up studies may focus on translating the intervention into additional languages.

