9. STUDY TIMELINES*

Aim 1: Patient participants will begin by completing a baseline survey which will take ~30 minutes or less. Stakeholder participants will complete a brief (~5-10 minutes) online demographics survey (study factsheet will be included in the REDCap survey). Both patient and stakeholder participation will involve completing a one-time interview session held by telephone or by webinar (**Please note: we will follow all COVID-19 related guidelines and precautions, favoring remote activity whenever possible**). Interviews are expected to last approximately

INVESTIGATOR STUDY PLAN - REQUIRED

60-90 minutes for patients and about 30 minutes for stakeholders. Participation will be considered complete following the conclusion of the interview. Medical record review will occur to assess annual LCS follow-up; record review may occur over several follow-up years (up to 4 years).

Aim 2: Patient participation will involve completing a baseline survey which will take ~30 minutes or less. Following the baseline survey, the intervention will include a telehealth support call (or multiple calls) (~20 minutes) if the participant feels it would be helpful (to practice using a video call or accessing their patient portal), and at least one video call with a tele-navigator (educational outreach call) (~10 minutes). Finally, participants will be asked to complete a follow-up survey (~20 minutes). Participation is expected to take place over approximately 3-6 months. Medical record review will occur to assess annual LCS follow-up; record review may occur over several follow-up years (up to 4 years).

A sub-set of patient participants and providers of patient-participants will be recruited to engage in a one-time in-depth interview which is expected to last approximately 60 minutes.

Study Timeline*: Work Plan and Deliverables

Quarterly Milestones									
Aim	Quarters	1	2	3	4	5	6	7	8
1	Material Development	X							
	Co-production		X	X					
	Stakeholder interview		X	X					
2	Recruitment				X	X	X		
	Data collection				X	X	X	X	
	Data analysis			X				X	X
	Manuscript							X	X
Grant Preparation								X	X

***Note:** We plan to conduct longer-term collection of clinical follow-up data and additional data analysis for ~2 additional years.

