25. LOCAL NUMBER OF SUBJECTS

Aim 1: We will recruit up to 50 participants for Aim 1. We aim to recruit a diverse sample of stakeholders including: patients (~6-12), PCPs (n~8), LCS navigators (n~7), LCS program leaders (n~8), Population Health leaders (n~6) and IT leaders (n~5).

Aim 2: Up to ~12 Aim 1 participants will be recruited to pilot test the intervention (but not enrolled in the Aim 2 intervention study). ~20 patients will be recruited to participate in the intervention. A smaller subset of ~5 intervention patients and ~5 providers whose patient participated in the study will be interviewed for in-depth feedback. Approximately 25 participants will be enrolled for Aim 2.

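### Section 13 names only means and SDs for outcomes that include yes/no measures, so the rates this pilot of about 20 patients is meant to estimate have no planned interval or stated denominator

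*Combined protocol and SAP*

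**What the plan says.** The quantitative plan in Section 13 is two sentences. The first has the scope "For measures of outcomes and intervention fidelity" and states that "we will present summary statistics with means and standard deviations of study variables". The second promises visualizations, including treatment cascades covering follow-up screening and communication after LDCT. Section 13 also names a mixed-methods pathway analysis, with no numerical summary attached.

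The power paragraph of the same section gives the aims as determining acceptability and to "estimate important process parameters (i.e. recruitment rates, completion rates of components) to inform a future study". On that ground it reports no sample size calculation. Section 25 gives the approximate size of the intervention group: "20 patients will be recruited to participate in the intervention".

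Among the Section 10 outcomes, one primary outcome is yes/no at each time point: "Adherence is defined as LDCT completion at 3, 6 and 12 months from the due date". One secondary outcome is also yes/no: "occurrence of patient-provider communication after LDCT". Another, communication modality, is categorical.

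Three further statements bear on denominators:
- The Aim 2 inclusion criteria in Section 6 require that the patient "Is overdue for LDCT follow-up".
- Section 9 offers the telehealth support call "if the participant feels it would be helpful", while Section 11 describes portal and video coaching without that condition.
- Section 11 says that Aim 2 enrolment uses purposeful sampling.

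No section mentions a confidence interval or a standard error, or states a denominator for any rate.

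**The concern.** Mean and SD can suit continuous measures such as staff time, cost, survey scores or a total fidelity score. For a yes/no outcome the SD is fixed by the proportion and n, so it adds nothing to the mean and barely changes with sample size. A study whose purpose is to hand rates to a later study should say how well it has estimated them. As written, the plan does not.

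The unstated denominators make this worse. Suppose a patient enters already more than three months past due and still without a scan. That patient cannot be adherent at three months, whatever the intervention does. If such patients stay in the denominator as failures, the adherence rate is pulled down by the entry criterion, and an interval around it would be centred in the wrong place.

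At stake is the use of the results. The future study would inherit rates without their uncertainty, and possibly an adherence rate that reflects how overdue patients were at entry.

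**Working it through.** **Inputs.** From the documents: about 20 intervention patients (Section 25), and the outcomes and clock in Section 10. The plan has no sample size, power or precision figure to reproduce. Assumed for illustration: the 95% level; every numerator; the denominators 15, 60, 100 and 200; and the numbers of patients (5 or 10) already past a time point at entry.

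**1. What the SD shows for a yes/no outcome.** For a 0/1 variable the sample SD is sqrt(p(1-p)·n/(n-1)).
- 16/20: sqrt(0.8 × 0.2 × 20/19) = 0.41; exact 95% CI 56-94%.
- 160/200: sqrt(0.8 × 0.2 × 200/199) = 0.40; exact 95% CI 74-85%. The larger n serves only to show the effect of sample size.
- 20/20: SD 0; exact lower limit 83%.

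The first two cases have almost the same SD, but the interval is about 38 percentage points wide in one and about 12 in the other. In the third, the SD suggests no uncertainty at all.

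**2. Precision with 20 patients.** The Clopper-Pearson lower limit is the 2.5% quantile of Beta(x, n-x+1) and the upper limit is the 97.5% quantile of Beta(x+1, n-x). At x = n the upper limit is 1.

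| Observed | Percent | Clopper-Pearson 95% CI | Wilson 95% CI |
|---|---|---|---|
| 10/20 | 50 | 27-73% | 30-70% |
| 12/20 | 60 | 36-81% | 39-78% |
| 16/20 | 80 | 56-94% | 58-92% |
| 20/20 | 100 | 83-100% | 84-100% |

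For context, Section 5 cites adherence of 16-59% in community programs and more than 80% in comprehensive ones. An observed 12/20 has an interval that overlaps both. A report of mean 0.60, SD 0.50 would not show this.

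**3. Recruitment rate.** The number invited is not given. With 20 enrolled, the exact intervals are:
- 60 invited: 33%, 22-47%.
- 100 invited: 20%, 13-29%.
- 200 invited: 10%, 6-15%.

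**4. Overdue at entry against a due-date clock.** If k of 20 enrol after a time point has passed without a scan, adherence at that point over all enrolled cannot exceed (20-k)/20.
- k = 5: ceiling 15/20 = 75%.
- k = 10: ceiling 10/20 = 50%.

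With k = 5 and nine scans completed by three months, adherence is 9/20 = 45% (23-68%) over all enrolled, but 9/15 = 60% (32-84%) among those whose three-month point was still open.

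The second figure is not clean either. A patient enrolled a few days before the three-month point stays in the 15 with almost no time to be scanned. The denominators at 3, 6 and 12 months would also describe different groups. Only a clock started at enrolment gives every patient the same time at risk.

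**The case against.** The best defence is that the plan is brief, not wrong. The mean of a 0/1 variable already is the proportion. The cascades are applied to follow-up screening and communication, the same two yes/no outcomes, and would normally show counts at each step. Feasibility is a primary outcome, so component completion can be read as falling under the means-and-SDs sentence. A reader given n could compute an interval. All of this stands, and it narrows the point: the recruitment rate is the only quantity that clearly has no named summary. It does not supply an interval or a denominator, and the reader's own calculation needs both n and the right denominator.

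It can also be said that no test, comparator or progression threshold depends on an interval, and that with purposeful sampling a binomial interval leaves out selection. Both are true, and they limit what the intervals can be used for. The stated goal is still estimation, for which precision is the relevant property.

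The due-date problem is, fairly, a matter of endpoint definition that adding intervals would not cure. It belongs here because it decides the denominator of a primary rate. Section 10 does let the adherence definition change with the pandemic, but it does not say that the due date is re-set for overdue patients.

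A reader might infer that the plan needs a power calculation, or that it would withhold proportions and counts altogether. The documents support neither. Omitting a power calculation is reasonable for a feasibility pilot, and nothing in Section 13 excludes n/N.

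**Conclusion.** The point holds as a recommended change to the analysis plan. It does not make the study invalid. The only named numerical summary does not convey precision for the yes/no outcomes, no interval is planned for any rate, and denominators are not stated. With 20 patients the unreported uncertainty is large: exact 95% intervals are about 46 percentage points wide at 50% and 38 at 80%.

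The adherence part is conditional. It applies if the due date is not re-set and if some patients enrol after a time point has passed. The documents do not say how overdue patients will be, so the ceilings of 75% and 50% show how the problem works and do not predict results. A reader might conclude that the adherence rate is certain to be biased downward by a known amount; the documents do not support that.

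**What to change.** In Section 13:
- **Continuous measures:** keep mean and SD, or median and IQR if skewed.
- **Binary outcomes, and recruitment and component-completion rates:** report n/N, percent and a 95% CI by one method named in advance (Clopper-Pearson or Wilson).
- **Categorical outcomes**, such as communication modality: report n/N and percent.
- **Denominators:** use invited or eligible patients (say which) for recruitment, and all enrolled for each component. Show the support call also among those who wanted it, once Sections 9 and 11 have been reconciled on whether that call is optional.
- **Adherence on the due-date clock:** report how many patients had passed each time point at enrolment, and do not count them as intervention failures.
- **Adherence on an enrolment clock:** also report LDCT completion by 3, 6 and 12 months from enrolment among all enrolled.
- **Interpretation:** state that the intervals cover binomial error only, because sampling is purposeful.

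The cost is some added wording, one extra adherence summary and little analysis time. No new data are needed: the due date is already required for the outcome, Section 30 has the consent date recorded, and Section 9 allows record review for up to 4 years. The downside is that results will look less certain, and the due-date denominators, especially at three months, may fall below 20.
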